4. STUDY TREATMENTS

4.1. Intervention arm

Participants will be randomised into different variants of an online CBT intervention, such that they receive different combinations of four different intervention components (at either high versus low levels, giving 16 different variants). All interventions include a default core common content (e.g., psychoeducation about RNT and CBT approaches to coping) so that all participants receive a minimal-level intervention (i.e., there is not a no-treatment control), delivered via the MyDataHelps digital platform. Participants will receive a course of online CBT designed to target RNT taking up to 16 weeks to complete, consisting of different randomised intervention components. Building on lessons from our previous trials^{53,54}, each intervention component will be present and interleaved throughout the entire course of therapy (rather than in discrete modules) to increase patient exposure to each ingredient and strengthen effective dose. See Section 5, Table 2, for an overview of the intervention components. Access to the online platform will remain available to participants during the follow up period for the study.

All participants will receive PWP(UK)/ coach(USA) support delivered via video conference/telephone and within the MyDataHelps platform (i.e., supported use of the intervention).

Participants will need to provide an email address to be set up with an account on MyDataHelps. There is evidence that supported digital interventions (i.e., those with support from a clinician or coach) outperform unsupported ones, with improved retention and adherence⁵⁵. In the UK, the support will be provided by psychological wellbeing practitioners (PWP), which is a well-established workforce for delivery of blended digital therapies used for low-intensity CBT in the IAPT Talking Therapies workforce.

The intervention will consist of 6 sessions in the MyDataHelps digital platform to be worked through over up to 16 weeks and supported by a minimum of 3 contacts with a PWP(UK)/ coach(USA). These contacts will typically last 20-30 minutes and focus on motivating, supporting and encouraging the participant to work through online material, dealing with any questions arising and tackling any problems or trouble-shooting.

The UK Psychological Wellbeing Practitioners (PWPs) will be certified via competency-based training at supporting digital interventions (e.g., behavioural activation) and managing risk. The USA coaches will have similar competency-based training in supporting digital interventions and managing risks. All PWPs and coaches will also be trained to be familiar with the content of the Calming Minds intervention, receive regular clinical supervision from an experienced clinician and will be trained to deliver all combinations of the intervention.

There will be standardised processes to ensure fidelity (including PWP self-rating of sessions). PWPs will follow up and reschedule sessions if missed or not attended by participant up to 3 times. It is planned that the minimum number of contact sessions would be 3, as detailed below. Participants can have additional sessions if needed up to a maximum of 6 sessions total.

- Session 1: An orientation session occurring close to when participant is set up on MyDataHelps to explain the intervention and to check the participant is able to access and use the platform, and to answer any questions.

- Session 2: A second session after the start of the intervention (after 1st online session is completed) to motivate ongoing use of the intervention as possible.
- Session 3: A third session approx. halfway through the intervention course (after 3rd online session is completed) to encourage participants to complete as much of the intervention as possible.

The trial management team will monitor the number of contact sessions with participants and online sessions started and completed, and maintain a record of inability to schedule sessions (with reasons) and sessions which were scheduled but unattended by the participant. The proportion of participants receiving less than 3 contacts for any reason during the intervention period will be monitored and reported.

USA-specific detail

In the USA, coaches will be undergraduate students or recent graduates who undergo local competency-based training similar to that provided for PWPs. Coaches are not equivalent to therapists and should not be referred to as such. Coaches will be supported by a local experienced lead clinician. The local trial management team at UCLA will monitor the number of contact sessions with USA participants and report to the lead team at University of Exeter for central oversight of contact session frequency.

Participants in the USA will have the option to access a Spanish translated version of the intervention in MyDataHelps, however coaching will only be available in English.

4.2. Control arm

There is no control arm in this study. All participants will be offered at least a minimum level of intervention in each of the different factorial variants described in section 4.1.

5. TRIAL DESIGN

This is an international factorial, randomised trial of a therapist-supported digital CBT intervention for people aged 18 and over with elevated RNT, with primary outcome collection at baseline, and at 16-weeks and 52- weeks post-randomisation. Participants and PWPs/coaches will be unblinded to the allocation.

A component-mechanism selection experiment using a balanced orthogonal factorial design will manipulate 4 components at high versus low levels (effect coded: high level coded +1 versus low level coded -1; 50% of sample randomized to high level of factor; 50% randomised to low level – see details in Section 4.1), to differentially engage respective mechanisms and test their causal effects on RNT (see Table 2)⁵⁶.

Factorial designs systematically experimentally manipulate multiple components or factors of interest simultaneously. Factorial designs have several advantages over comparative RCTs, component (dismantling or additive) designs, and single factor designs⁵⁶.

In effect-coded analysis of a balanced 2^k factorial experiment (in contrast to dummy coding), we have equal power to detect any regression coefficient of a given size (main effect or interaction), the main and interaction effects are completely uncorrelated, and the presence of interaction effects does not

reduce power for the estimation of main effects. In a factorial mediation analysis, a joint significance test (causal steps approach) enables us to test if a manipulated component/ingredient changes RNT and changes each putative mediator and if each assessed putative mediator is associated with change in RNT⁵⁷.

We hypothesize that at least one of the intervention components will be an active ingredient such that the presence of that component will outperform absence of that component in reducing RNT across 16 weeks in a high RNT adult sample.

We further hypothesize that at least one of the intervention components will be an active ingredient such that the presence of that component will outperform absence of that component in reducing anxiety (GAD7) and depression (PHQ-9) across 16 weeks in a high RNT adult sample.

Based on the benefits of the design, we will explore whether there are any two-way interactions between components such that their combination has either additional benefit or reduced benefit relative to their occurrence alone.

Table 2: Illustrative example of factorial trial (4 factors=2⁴) to test mechanisms to reduce RNT

Conditions	Increased specificity & concreteness (Be Specific)	Manipulated			Fixed	
		Targeting RNT as a habit (Break Habit)	Self-compassion (Be Kind)	Absorption in direct experience (Be Present)	Psychoeducation	
1.	-1	-1	-1	-1	+1	
2.	+1	-1	-1	-1	+1	
3.	-1	-1	+1	-1	+1	
4.	+1	-1	+1	-1	+1	
5.	-1	-1	-1	+1	+1	
6.	+1	-1	-1	+1	+1	
7.	-1	-1	+1	+1	+1	
8.	+1	-1	+1	+1	+1	
9.	-1	+1	-1	-1	+1	
10.	+1	+1	-1	-1	+1	
11.	-1	+1	+1	-1	+1	
12.	+1	+1	+1	-1	+1	
13.	-1	+1	-1	+1	+1	
14.	+1	+1	-1	+1	+1	
15.	-1	+1	+1	+1	+1	
16.	+1	+1	+1	+1	+1	

Note. Every manipulated component factor occurs an equal number of times at high and low levels (i.e., balanced). Effect coded; for each component factor 50% of participants are randomised to high level (coded +1) and 50% randomised to low level (coded -1). All factors are orthogonal to each other, except for psychoeducation about RNT and coping, which is the default element common to all conditions received by participants.

5.1. Design considerations for minimising bias

5.1.1. Randomisation

Randomisation will be in equal allocation (i.e., 1:1 for high level versus low level for all factors) using an independent computerised randomisation programme (REDCap Academic). The randomisation system and randomisation code will be designed and written by the senior statistician at ExeCTU. Randomisation will be stratified by location (UK versus USA) and those above or below caseness on PHQ-9 (depression; PHQ \leq 9 versus >9) or GAD7 (anxiety; ≤ 9 versus >9) to investigate acute treatment versus prevention.

PWP (UK) / coach (USA) allocation will be independent of randomisation to treatment arm and occurs with allocation concealment i.e., selection of next PWP/coach to take on next randomised patient occurs before the randomisation of next patient is known; all PWPs/coaches will provide all 16 variants of the intervention, with the assumption that, given the large numbers randomised, this will become balanced over the course of the study, with this balance monitored and adjusted if necessary - to ensure that the main effects of intervention factors are independent of PWP/coach allocation.

USA-specific detail

The USA will utilise a separate but equivalent parallel randomisation system (REDCap Academic) to that used in the UK, with a separate randomisation list provided by ExeCTU (UK).

5.1.2. Blinding

As is common for psychotherapy studies, neither study participants nor PWPs/coaches will be blind to treatment condition allocation – although given the factorial trial and that all participants receive a variant of internet CBT, participants may not necessarily be knowledgeable of the specific components being manipulated.

Outcome assessors (e.g., members of the study team who support participants with questionnaires over the telephone or follow-up on automated data collection, where necessary) and trial managers will be blind to treatment allocation. If an outcome assessor becomes unblinded then they will be replaced by an alternative researcher, where possible and this will be documented. All unblinding incidents will be reported to the oversight committees in routine reports. Because all participants will receive a variant of the intervention the impact of outcome assessor unblinding on outcome integrity is likely to be very low.

The trial statistician completing the analysis will be blinded throughout, while the senior statistician will be unblinded after the statistical analysis plan is signed off.

The qualitative interviewer and members of the process evaluation team will be unblinded, as they will sample and interview participants about mechanisms based on treatment allocation amongst other sampling criteria.

USA-specific detail

The blinding plan is equivalent in the USA, with exception that the trial statisticians and qualitative interviewer are based in the UK and equivalent roles will not be performed at UCLA.

6. STUDY SETTING

This is a multicentre study, with nationwide recruitment in the UK (led from University of Exeter, UK) and recruitment from Imperial Valley Community College in the USA (led by UCLA, USA).

The study will be delivered online, with the intervention supported by virtual contact with trained PWPs/coaches (phone or video call or messaging). Participants will self-screen, provide informed consent and complete baseline and follow-up outcome data using REDCap Academic and the mPath App (for EMA and online micro-assessments). The intervention will be delivered using the MyDataHelps digital platform.

[name], at the University of Exeter will lead the study and recruitment in the UK, with a team of research fellows and trained PWPs and with support from the Exeter Clinical Trials Unit (ExeCTU).

A central trial manager based at ExeCTU will be responsible for monitoring study progress at all sites.

USA-specific detail

The Co-Investigator, [name] at UCLA shall lead recruitment in the USA, and manage the local research team with providing the coach support, risk management and monitoring local study progress (recruitment, treatment progress, retention) and ensuring all relevant local permissions have been gained.

UCLA hold the licence to the MyDataHelps platform.

7. PARTICIPANT ELIGIBILITY CRITERIA

7.1. Inclusion criteria

Participants must satisfy ALL of the following criteria to be enrolled in the study, and will be excluded in sequence if an individual does not meet a criterion during screening (to minimise participant burden):

1. Lives in the UK or USA
2. Aged 18 and over
3. Access to a suitable smart phone/device to use the m-Path app and MyDataHelps intervention (i.e. MyDataHelps requires iOS 16.4 or later. iOS 16.4 is compatible with all iPhone models starting from the iPhone 8 and later. For Android devices, MyDataHelps requires Android version 8.0 or higher.)
4. Elevated RNT based on the following assessment scores – scoring in top quartile in one and in top tercile for the other based on prior studies:
 - RRS brooding⁴⁰ score above 12 (top quartile) and PSWQ-short form⁴¹ score above 24 (top tercile) OR
 - RRS brooding⁴⁰ score above 11 (top tercile) and PSWQ-short form⁴¹ score above 26 (top quartile)

7.2. Exclusion criteria

Participants who self-report meeting ANY of the following criteria at time of recruitment will be excluded from study participation:

1. Concurrent psychotherapy
2. Current self-reported diagnosis of any of the following conditions, including receiving or waiting for treatment:
 - Alcohol abuse/dependence
 - Substance abuse/dependence
3. Self-reported diagnosis of current or history of bipolar disorder or psychosis at any time
4. Taking antidepressants or anxiolytic medications at a stable dose for less than six weeks
5. Severe post-traumatic stress disorder (PTSD, assessed as a score of 17 or higher in total for the first six questions AND a score of 2 or higher on the seventh question of the adapted International Trauma Questionnaire⁵⁸; ITQ)
6. Suicidal thoughts and self-harm assessed by a combination of PHQ-9³⁸ **question 9** score of 1 or higher and a yes to question R1a and/or R1B, and a yes to either question R2 and/or R3 (detailed below):
 - *R1a = In the last 2 weeks have you been experiencing regular thoughts about suicide?*
 - *R1b = In the last 2 weeks have you been experiencing regular thoughts about self-harm?*
 - *R2 = In the last 2 weeks have you had any intention to hurt or kill yourself?*
 - *R3 = In the last 2 weeks have you made any plans to harm yourself or end your life?*

People who are excluded from the study will be provided with information signposting them to relevant advice or support. If a person indicates that they have intention to, or made plans to, hurt or kill themselves in the past 2 weeks the screening form will enable the person to volunteer their contact details and GP details if they would like to receive a phone call from a member of the research team, and potentially be referred to their GP.

The PWPs will follow a separate risk management protocol to assess and support any individuals who are identified as being at risk during the study.

USA-specific detail

For participants recruited in the USA, automated signposting to support services will be tailored to services specific to the local study population in the USA.

During screening, if individuals endorse the exclusion criteria of active suicidality, severe PTSD or diagnosis of bipolar disorder, substance abuse or psychosis they will be provided with contact information for the college health center counseling services, as well as community emergency resources.

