The initial screening process for the study will exclude anyone reporting current or past severe psychiatric disorder (current or past diagnosis or treatment for psychosis or bipolar disorder; current severe PTSD or alcohol/substance abuse or dependence) and those reporting elevated suicidality (scoring 1 or more on item 9 of the PHQ-9 and then answering yes to automated follow-up questions asking about plans or intentions regarding suicide). The screening tool will automatically signpost these individuals towards appropriate guidance and help, including general information on the presenting symptom, recommended actions to keep themselves safe, advice to seek medical help from their GP or relevant local clinician/service and direct links to relevant national sources of help. The form will enable the person to volunteer their contact details and GP details if they would like to receive a phone call from a member of the research team, and potentially be referred to their GP. Excluded individuals will still be able to access other treatment outside the study.

Participants who report risk (e.g. suicidal thoughts) or significant worsening symptoms on the follow-up assessments or during contacts with PWPs will also receive automated messaging recommending actions and signposting. Significant worsening symptoms is defined as a deterioration of movement across two or more score categories on the GAD7 or PHQ-9 from baseline to 16-weeks or from baseline to 52-weeks follow-up. At the point of automated signposting, participants can request contact from a study PWP or contact a study PWP via e-mail or telephone to seek advice. PWPs will follow standard risk management protocols that include contacting the individual, assessing their situation and status (e.g., standardised checklist concerning suicidal or self-harm thoughts, plans, intentions, preparation, barriers, and safety measures), providing safeguarding, safety plans and guidance, and, as necessary, referring to relevant clinical services, including contacting participants GP, crisis teams, or acute emergency services as necessary. This procedure has been successfully used in prior trials which received ethical approval including both local institutional approval and NHS approval.

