For screening, individuals will complete an online survey of the eligibility criteria. Screening will be step-wise, so if a person is excluded on a criterion, they will not need to complete any further questions. Screening questions will be presented in order of seriousness (starting with the least serious) to avoid asking potentially distressing questions if a person is clearly ineligible (e.g. under 18 years old or does not meet the criteria for RNT). The screening process will include completing the RSS, PSQW short form and PHQ-9 validated questionnaires and if a person is eligible and consents to take part, the data from these questionnaires will be included as baseline data so participants do not have to repeat the questionnaires. Screening data will be self-reported. The research team will not undertake checks with healthcare services to verify the data provided is accurate (e.g., will not check for a diagnosis of depression or bipolar disorder in an individuals' medical record). The screening form will not collect personal identifiable data other than email address for purposes noted above, however some non-identifiable demographic data (age and self-reported gender) will be collected at screening so we can monitor whether the study is disproportionately screening out individuals from a particular demographic. If a potential participant clicks away from the screening process they will be sent a link by email which they can follow to return to the survey later.

Potential participants who, after self-screening, meet all the inclusion criteria and none of the exclusion criteria will be invited to provide informed consent to take part in the study. This will be electronic consent via REDCap Academic (see section 8.2 Consent).

USA-specific detail

UCLA will not utilise the UK landing webpage. Interested individuals will navigate directly to the REDCap Academic which will contain the PIS, video and screening forms.

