12. SAFETY MONITORING

There is no known health risk associated with any of the assessments or the CBT modules included in the intervention. As such, the risk associated with participation in this study is deemed to be low. Further, we anticipate that the interventions will on average reduce symptoms and improve well-being. CBT is a widely used intervention in NHS and non-NHS settings.

The initial screening process will exclude anyone self-reporting a history of severe psychiatric disorder, alcohol/substance abuse and those reporting elevated suicidality. These individuals will be automatically guided towards appropriate information and sources of help. This process means that individuals likely to have significantly increased risk (e.g., for self-harm and suicidality), and/or for whom more intensive psychological and psychiatric treatment is appropriate, will not be included in the study.

Other than the intervention failing to produce an effect, there is nothing in the literature to suggest possible adverse effects of the assessments and interventions for the participants involved. Versions of components within the intervention have been previously used with no detected harmful effect.

As with all psychological interventions, individuals reflect on their difficulties, which can produce temporary increases in distress, but no more than would commonly occur in daily life. The likeliest outcome for users who do not find the intervention of benefit, or who do not get on well with the assessments, is their disengagement from it. In addition, all participants receive more intensive monitoring, with processes to identify and direct all relevant participants to potential sources of help.

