As part of our policy for addressing risk and prioritising the welfare of participants, participants are provided with links to online support, the opportunity to request contact from the study team, and automatic signposting to help and guidance if reporting risk (e.g., suicidal thoughts, as indexed in items within the Patient Health Questionnaire-9 (PHQ-9) on the screening or follow-up questionnaires) or significant worsening symptoms suggesting a need for help. These messages include general information on the presenting symptom, recommended actions to make themselves safe, and advice to seek medical help, and direct links to relevant national sources of help. These sources of support will be tailored by participating country. For this purpose, significant worsening symptoms is defined as a deterioration of movement across two or more score categories on the GAD7 or PHQ-9 from baseline to 16-weeks or from baseline to 52-weeks follow-up. At the point of automated signposting, participants can request contact from a study PWP or contact a study PWP via e-mail or telephone to seek advice.

The main indicator of harm will be the completion of the PHQ-9 questionnaire by the participants at baseline and at 16-weeks and 52-weeks post-randomisation. Questionnaires will be automatically screened for signs of severe distress (for example, defined reports of suicidal ideation), with automatic programmed questions following up to ascertain aspects of risk and to automatically provide users

with recommended advice and signpost towards help (GP, local hospital, crisis teams, relevant charities; e.g., website link to the Samaritans). Other indicators would be reports of worsening symptoms or suicidality in direct contact from participants to the research team or in contact with the study PWP (UK)/coach (USA). For participants at 16-weeks, elevated reports of suicidality (as per definition at screening, i.e., endorsing automated follow-up questions 2 or 3) will be followed up by the associated PWP, following an established risk protocol.

PWPs/coaches will maintain a risk log separate from the research database to document interactions with participants who are (or potentially are) 'at risk' and any actions taken to support, guide and/or refer them on to other services. The risk log will not be considered 'research data', but instead will be data pertaining to the clinical care of the participant

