13.3. Statistical analysis plan

Analysis will be undertaken in line with the factorial trial extension to the CONSORT agreement for the reporting of trials⁶⁹. Primary inferential analyses, using a treatment policy estimand, will compare the main effects across outcomes using multilevel mixed models adjusting for baseline score, first order interactions, and PWP/coach effect (random effect).

The extent of missing data will be considered and where necessary, in agreement with Trial Steering Committee (TSC), imputation methods will be used (led by co-investigator [name]) to handle missing data whilst minimising bias. These assumptions will further be tested through a sensitivity analyses.

The study statistical analysis plans will be prepared before any formal analyses and reviewed and approved by Data Monitoring and Ethics Committee (DMEC) and TSC. The trial statistician will remain blind to allocation until primary analyses are completed. However, given the complexity of this study and to facilitate communication with the DMEC the senior statistician ([name]) will be unblinded once the Statistical Analysis Plan (SAP) is approved by the DMEC and TSC and has been signed off with the intention that this is achieved prior to the randomisation of the first participant.

13.3.1. Summary of baseline data and flow of patients.

The baseline data being collected in the study is summarised in the Schedule of Events (Table 3). The eCRF for the collection of the baseline data is available as a separate approved document. The baseline data will be collected after the screening and consent, other than those items listed under the 'eligibility screen' heading which will be collected as part of the screening survey. The measures are detailed fully in separately approved assessment documents for the various timepoints. The flow of patients throughout the study is outlined in Figure 1.

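### The suicidality exclusion in Section 7.2 requires regular thoughts as well as intention or plans; Sections 2 and 12 describe the same exclusion without that condition

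*Protocol*

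**What the plan says.** **Section 7.2, criterion 6**, the operative eligibility rule, joins three conditions: PHQ-9 item 9 of 1 or higher, "and a yes to question R1a and/or R1B, and a yes to either question R2 and/or R3". All four questions cover the last two weeks. R1a asks about regular thoughts of suicide, R1b about regular thoughts of self-harm, R2 about any intention to hurt or kill oneself, and R3 about plans to do so.

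**Section 2** describes the screening exclusion for elevated suicidality as item 9 of 1 or more and then "answering yes to automated follow-up questions asking about plans or intentions regarding suicide". It names no regular-thoughts question.

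**Section 12** says screening will exclude people with "alcohol/substance abuse and those reporting elevated suicidality", and assures the reader that this keeps out "individuals likely to have significantly increased risk (e.g., for self-harm and suicidality" among its examples. For the 16-week follow-up it refers to "elevated reports of suicidality (as per definition at screening, i.e., endorsing automated follow-up questions 2 or 3", again without R1.

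**Table 3, note f**, makes the additional risk questions depend on item 9 alone.

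**Section 8.1.1** describes step-wise screening, "so if a person is excluded on a criterion, they will not need to complete any further questions", with questions ordered from least to most serious. It also states: "The research team will not undertake checks with healthcare services to verify the data provided is accurate".

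**The concern.** The protocol gives two rules for one safety exclusion, and the section that governs eligibility holds the more permissive one. Under 7.2 as written, a person who reports having planned to end their life in the past two weeks may enter the trial if they answer no to both questions on regular thoughts. Section 2 says that person is excluded, and Section 12 assures readers that screening keeps out people at significantly increased risk.

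Screening is self-completed online and is not checked with healthcare services. Whatever expression is programmed in the two separate REDCap instances therefore decides who is eligible. An eligible person then spends at least 10 and normally up to 28 days in baseline (Table 3, note g), and Section 12.3 limits safety monitoring to randomised participants. In the USA, the crisis contact details given at screening are tied to endorsing the exclusion criterion (Sections 2 and 7.2), so the choice of rule may affect that step too.

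**Working it through.** The protocol gives no figure to reproduce here; the check is logical.

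**Inputs.** Four yes/no answers (R1a, R1b, R2, R3), given item 9 of at least 1. If item 9 is 0, neither rule excludes.

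- Rule A (Section 7.2): (R1a or R1b) and (R2 or R3).
- Rule B (Section 2, and Section 12 read together with the item 9 trigger): (R2 or R3). This takes Section 2 to mean yes to at least one of the two questions, in line with the word *or* in Section 12.

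**Count of answer patterns.**

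- All patterns: 2^4 = 16.
- At least one yes on R1a/R1b: 2^2 − 1 = 3 of 4. The same holds for R2/R3: 3 of 4.
- Rule A excludes 3 × 3 = 9.
- Rule B excludes 4 × 3 = 12.
- Difference: 12 − 9 = 3.

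The three patterns that differ:

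| R1a | R1b | R2 (intention) | R3 (plans) | Section 7.2 | Section 2 |
|---|---|---|---|---|---|
| no | no | no | yes | eligible | excluded |
| no | no | yes | no | eligible | excluded |
| no | no | yes | yes | eligible | excluded |

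Enumerating all 32 patterns, with item 9 also free, gives the same three disagreements and no others. Each goes the same way: 7.2 admits, Section 2 excludes.

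**Can these patterns arise?** Only if R2 and R3 are shown to someone who answered no to R1a and R1b. Four places bear on this:

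- Table 3, note f, triggers the risk questions on item 9 and mentions no further gate.
- Section 7.2 itself offers a research-team call to anyone reporting intention or plans, with no R1 condition.
- The step-wise rule in 8.1.1 stops the questions once a person is excluded. A no to R1 does not exclude anyone, so this rule does not remove the case.
- The least-serious-first order in 8.1.1 is compatible with a gate but does not state one.

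Section 13.3.1 notes that "The measures are detailed fully in separately approved assessment documents for the various timepoints". Those documents are not available here, so a gate cannot be ruled out. With a gate, the three patterns cannot be recorded and the two rules coincide. The gate would create a different gap, however: a person with a plan but no regular thoughts would never be asked about the plan.

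**After the change.** With R1 removed from criterion 6, Rule A equals Rule B and the disagreements fall from 3 to 0.

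**The case against.** The strongest reply is that 7.2 is the designated eligibility section and sets out the questions and the logic in full, whereas Section 2 is a risk summary that paraphrases loosely. It speaks only of suicide, for example, although R2 and R3 also cover self-harm. The Section 12 wording is shorthand: it omits item 9 as well as R1, its reference to questions 2 or 3 presupposes a question 1, and it governs 16-week follow-up, where nobody is excluded. The general statements in Section 12 set no rule. A sequence of item 9, then R1, then R2/R3 would reconcile every section and leave nobody affected. The call offered in 7.2 would in any case reach anyone who reports intention or plans. If 7.2 is what was intended, aligning the other sections to it would be the smaller change.

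Much of this is fair. Section 12 is supporting evidence only, the frequency is unknown, and the contact offer limits harm, as do PWP or coach training in risk management (Section 4.1) and possible withdrawal of someone found ineligible (Section 11). None of it removes the contradiction between Section 2 and Section 7.2. The reconciling sequence is stated nowhere, and the two places that describe triggers do not include it. An offer of contact does not decide eligibility. Aligning the text to 7.2 would give one rule, but it would keep the permissive one and leave the assurance in Section 12 unsupported for the people in question.

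**Conclusion.** The concern holds. Section 7.2 and Section 2 give different answers for a person positive on item 9 who reports intention or plans but denies regular thoughts, and Section 12 sides with Section 2. The extent is 3 of 16 answer patterns. That is a statement of logic and says nothing about how many people would be affected, which the protocol does not allow anyone to estimate.

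Confidence is high that the texts conflict as written. It is medium that the case can occur in practice, because the survey branching is not in the protocol. The estimand, power and primary analysis are untouched. It should still be fixed: this is a safety-relevant eligibility rule, and the text that governs entry is the one that fails to deliver the protocol's own assurance.

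**What to change.** Subject to confirmation by the clinical leads:

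1. Change criterion 6 in Section 7.2 to: PHQ-9 item 9 of at least 1 AND (R2 or R3).
2. Present R2 and R3 to everyone with item 9 of at least 1, whatever the answer to R1.
3. Reword Section 2 so that it covers self-harm as R2 and R3 do.
4. Check that the UK and USA REDCap builds both use this one expression.
5. If recruitment has begun and R2 and R3 were asked regardless of R1, list randomised participants with item 9 of at least 1, no to both R1 questions and yes to R2 or R3, for clinical review.

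**Cost.** There will be some additional exclusions, probably few but not quantifiable from the protocol, and possibly two more screening questions for people positive on item 9. A protocol amendment is needed. Because an eligibility criterion changes, the sponsor may class it as substantial. Under Section 17.10, TSC approval would then be sought before REC or HRA submission, and UCLA IRB approval is needed for the USA. The rest is a logic check in two databases and, if recruitment is under way, one listing.
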